participants so far. Follow-up counseling/referral phone calls were successfully placed for all detected openings and only four were not reached within 24 hours. All participants successfully reached for follow-up reported having taken the test **minutes** after opening it, suggesting that monitoring the kit's **opening** serves as a reasonable marker of when they **took** the test. Figure 3 shows study outcomes to date. These data show that 96% of those in the eTEST group have tested for HIV at some time during the study period, compared with 90% for standard HBST, and 62% for control. Among the 63% of participants who have completed Month 5 of the study, repeat testing rates (reporting testing during **both** of the first two 3-month periods) were 92% in eTEST, 54% in standard HBST, and 46% in control. Rates of testing for other STIs were modestly higher in the HBST conditions, but this difference is difficult to interpret due to the small sample size and may not be meaningful.

Over 72% of eTEST participants received risk reduction counseling during the study period (control=18%, standard HBST=15%). While PrEP was not an explicit focus of the follow-up phone calls, 25% of eTEST participants reported having consulted with a physician about PrEP and 10% reported having started PrEP as a result, compared with 4% who sought consultation and started PrEP in the control group. While AA and H/L participants comprised only 21% of this sample, over 75% of those assigned to HBST conditions tested for HIV at some point during the study period, compared with 43% in the control condition. Moreover, 67% reported testing during both the first two quarters of the study so far, compared with 33% in the control condition.

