**Specific Aim 1:** To test whether the eTEST intervention results in higher rates of (a) initial and follow-up HIV testing, and (b) receipt of additional prevention services after testing (e.g., STI testing, risk reduction counseling, safer sex supplies) compared with standard HBST and reminders for clinic-based testing among MSM in three US regions with large AA and H/L MSM populations. As an exploratory aim, we will also examine whether receiving HBST helps detect more infections during the study period and reduces the time to diagnosis among those receiving reactive results, compared with clinic-based testing alone.

**Specific Aim 2:** To test whether providing focused information/counseling about PrEP during eTEST contacts results in more participants (a) consulting with medical providers about PrEP and (b) initiating PrEP. We will define a PrEP care continuum, including the number of MSM who meet clinical indications for PrEP, the number who are interested in and are linked to care, the number who are prescribed PrEP, and the number who initiate PrEP in each condition.

**Specific Aim 3:** To assess the cost-effectiveness of the eTEST system for improving rates of HIV testing compared with clinic-based testing alone. We will use mathematical models to estimate whether the eTEST system (and HBST) can be cost effective under various scenarios (e.g., testing intervals).

The proposed research will provide a robust test of the feasibility, efficacy, and value of home-based testing programs with post-test follow-up in communities with large populations of AA and H/L MSM that are highly affected by HIV. It is also among the first studies in the US to leverage HBST to engage difficult-to-reach populations in care. Results can also inform efforts to seek high-risk MSM and engage them in PrEP services.

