**Overview of Research.** Given these issues, the proposed research involves conducting a fully-powered efficacy test of HBST and the eTEST system's effects on rates of any/repeat HIV testing, use of other prevention services (e.g., STI testing, HIV risk reduction counseling), and PrEP linkage/initiation, compared with "standard" HBST and reminders for clinic-based testing, among high-risk MSM in three regions in the US: The Deep South (Jackson, MS), West Coast (Los Angeles), and Northeast (Providence/Boston). High-risk MSM ( $N=2000$ ,  $N=666$  per metro) who have not tested in the last year will be recruited online using an interactive web application. Participants will be randomly assigned to one of three arms that involve receiving one of the following at baseline, 3, 6, and 9 months: (1) HBST with phone follow-up (eTEST condition), (2) standard HBST (no follow-up), or (3) reminders for clinic-based testing only (control). Only enhanced eTest participants will be provided with the eTEST app, which will monitor the status of HBST kits and facilitate phone follow-up. Control participants will receive text messages at quarterly intervals, reminding participants to get tested in a clinic. Participants in the standard HBST condition will receive their HBST in the mail when it is time for their quarterly tests. All study participants will have access to information that may be generally helpful (e.g., information about HIV, testing, and a testing clinic locator) and are already publicly available. Throughout the study, all participants will complete online questionnaires assessing key outcomes each quarter, which will be confirmed by reviewing clinical records in each local area when possible. Analyses will assess eTEST's efficacy within and across regions, as well as the cost-effectiveness of these strategies compared with relying on clinic-based testing alone.

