## Planned Analyses

Analyses will be conducted in Year 5. To evaluate Aim 1(a), we will use factorial logistic regression to test whether rates of having completed any HIV test over the 12 month study period (assessed via self-report and/or clinic records) differ by study condition. Condition, study site (and their interaction) and other relevant covariates will be entered as predictors, allowing us to explore whether each condition's effects differ by study site. To explore the effects of study condition on regular HIV testing, we will use a generalized estimating equation (GEE) for repeated, binary outcomes, specifying whether participants tested during each 3-month study period as the focal outcome. A logit link function and independent correlation structure will be specified, with study condition, site, and relevant covariates as predictors, to test whether the odds of testing differ across time period, condition, and site. GEEs are a fitting approach for studies in which correlations between repeated measures variables are to be controlled, rather than a central focus of the analysis. For all models of **HIV testing** outcomes, a covariate reflecting whether a given participant had initiated PrEP (and when, for longitudinal models) will be added to each model, since these individuals are required to test for HIV quarterly as a part of ongoing PrEP care. Doing so will allow us to estimate the effects of study arm on HIV testing among those who did not initiate PrEP. Given that we have proposed collecting 54 more participants per site (162 total) than is required to estimate our most complex model (see Model 1b in Section 3C.3.10), we believe we will be fully powered to test this model, even with a high rate of PrEP adoption. While contamination of the control group in our pilot study was rare (only one control participant reported using a HBST), we will also track **where** each participant tested (at home, in person) in quarterly surveys. If contamination is significant, we will employ methods aimed at reducing this bias, including adding indicators of contamination as covariates or bootstrapping. To evaluate Aim 1(b), we will generate variables reflecting whether participants received testing for other STIs or risk reduction counseling during each of the four 3-month intervals of the study period. Similar GEE models will be estimated for these outcomes with time period, condition, and site as predictors, to test whether the odds of receiving each service differ across these factors. To evaluate Aim 2, we will code variables indicating whether participant reports or clinic records reflect participants having consulted with a medical provider about PrEP and/or received a PrEP prescription any time across the study period. Factorial logistic regression with study site, condition, and their interaction will be entered as predictors of this outcome, to test whether the odds of having received consultation and/or a PrEP prescription differ across each of the study sites and conditions. Overall, data from those who drop out or withdraw from the study will be used in these analyses, in intent-to-treat (ITT) fashion. Similarly, we will assume values of zero for all outcomes (i.e., non-receipt of testing or services) when quarterly assessments are missing but participants are retained in the study. Depending on the degree of missing assessments, we will use multiple imputation for these values, since data from missing assessments will likely be missing not at random.

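### Aim 1(a) promises follow-up testing results, but its only analysis of them, a quarterly GEE, can be significant on one-off tests alone

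*Combined protocol and SAP*

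**What the plan says.** Specific Aim 1 (section B.1) is to test whether eTEST gives "higher rates of (a) initial and follow-up HIV testing". The Overview of Research in the same section lists effects on "rates of any/repeat HIV testing, use of other prevention services" among what the trial will test.

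Planned Analyses (section B.4) gives two models for HIV testing:

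- Factorial logistic regression on "rates of having completed any HIV test over the 12 month study period", with condition, site and their interaction.
- A logit-link GEE with independence working correlation, "specifying whether participants tested during each 3-month study period as the focal outcome". It is introduced as a way to explore regular testing and is specified "with study condition, site, and relevant covariates as predictors, to test whether the odds of testing differ across time period, condition, and site". Time period appears in the purpose of the model but not in its list of predictors, and no condition-by-period term is stated. The text treats within-person correlation as something to control for, not as a target.

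No outcome counts participants who test more than once. The pilot, described in B.1, did have one: testing in both of the first two quarters. Its rates "were 92% in eTEST, 54% in standard HBST, and 46% in control".

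**The concern.** Repeat testing is a property of a participant: did this person test again? The GEE models the proportion tested in each quarter and does not ask whether the same people make up that proportion each time. An arm that gets more people to test once raises the quarterly average just as an arm that gets the same people to test again does.

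At stake is the follow-up half of Aim 1(a). A significant condition effect could be reported as more regular testing when the arms differ only in one-off tests. A real difference in repeat testing could also leave the quarterly averages equal. The any-test analysis is not affected.

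**Working it through.** **The plan's own figure.** The plan gives no figure for this point. The 246 in Power Considerations rests on a table that is not in the available text, so it cannot be rebuilt. Only its arithmetic checks: 300 − 246 = 54 per site, and 3 × 54 = 162. Nothing below depends on it.

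**Inputs.** Four quarters (Power Considerations). Any-test rates of 90% (standard HBST) and 62% (control) come from the pilot in B.1. Arm sizes are 2000/3 ≈ 667, from the stated total, and 3 × 300/3 = 300, from the 300 per site in Power Considerations. Both are shown because the documents give both. Assumed: 1:1:1 allocation, two-sided 0.05, and the splits between one-off and repeat testers below.

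**1. What the GEE targets.** Let N be the number of quarters (0–4) in which a participant tested. Then

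mean quarterly proportion = [P(N≥1) + P(N≥2) + P(N≥3) + P(N≥4)] / 4.

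First tests enter as P(N≥1)/4. A 28-point any-test gap (90 − 62) therefore moves the mean by 28/4 = 7 points with no difference in repeat testing.

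**2. First tests alone.** If every tester tests exactly once, the quarterly means are 0.90/4 = 22.5% and 0.62/4 = 15.5%. The odds ratio is (0.225/0.775)/(0.155/0.845) = 1.58, with no repeat testing in either arm.

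**3. Equal repeat rates, any-test 90% v 62%.** Because the planned GEE uses independence working correlation, its robust test is close to a comparison of mean N.

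- *20% repeaters in both arms.* P(N = 0,1,2,3,4) is .10, .70, .10, .05, .05 v .38, .42, .10, .05, .05. Mean N is 1.25 v 0.97 and the variance is 0.7875 v 1.1291. Quarterly means are 31.25% v 24.25%, odds ratio 1.42. At 300 per arm, SE = √(1.9166/300) = 0.0799, z = 0.28/0.0799 = 3.50, and the chance of rejection is Φ(3.50 − 1.96) ≈ 94%. At 667, z = 5.22, above 99.9%.
- *46% repeaters in both arms, spread evenly over 2, 3 and 4 quarters.* Mean N is 1.82 v 1.54 and the variance is 1.574 v 2.235. Quarterly means are 45.5% v 38.5%, odds ratio 1.33. At 300 per arm, z = 0.28/√(3.809/300) = 2.48, about 70%. At 667, z = 3.71, about 96%.

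Simulation of the GEE (condition and period main effects, robust SE, 1,000 runs, no site terms) agrees: 93.5% and 100% in the first case, 70.0% and 96.2% in the second. In the same runs, a test of N≥2 rejected in 4.9–5.8%.

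**4. The reverse.** If 96% of one arm test once and 24% of the other test in all four quarters, both average 24% per quarter. The GEE odds ratio is about 1.0 and it rejects in 5–6% of runs, while repeat testing is 0% v 24%.

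**5. Both planned models together.** From step 1, 4 × mean − any = P(N≥2) + P(N≥3) + P(N≥4). Over two quarters the right side would be the repeat rate itself. Over four it is a sum of three terms. Example: one arm has 90% testing exactly twice (mean N = 1.8). The other has 60% testing once and 30% four times (0.6 + 1.2 = 1.8). Any-test is 90% in both and the quarterly mean is 45% in both, but N≥2 is 90% v 30%. If tests are spread evenly over quarters, a condition-by-period term sees no difference either.

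**6. Power for a repeat outcome.** Using 54% v 46% for illustration, n per arm = (1.96√0.5 + 0.8416√0.4968)²/0.08² = 613 for 80% power. Power is about 83% at 667 per arm and 50% at 300. Within one site it is about 39% at 222 per arm (2000/9) and 20% at 100 per arm (300/3).

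**The case against.** The proportion of quarters with a test is a sound measure of frequency in a trial that offers testing every three months, and the plan says only that this model will explore regular testing. That stands: the GEE is valid for what it estimates. But Aim 1 is worded as a test, and no other planned analysis addresses follow-up testing.

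The two models can be read together, and in step 4 the any-test model does separate the arms (96% v 24%). That also stands in part, but step 5 shows the recovery is incomplete over four quarters, and no test of the combination is planned.

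Time period is named in the purpose of the GEE, and the parallel Aim 1(b) models list it as a predictor, so period is probably intended. A period main effect does not separate arms by quarter, however. The unstated interaction would help if first tests cluster early, but not if they are spread out.

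The influence of first tests is bounded. True: 7 points on the pilot any-test gap, so a much larger quarterly gap would need repeat tests. Step 3 shows that 7 points is enough for significance.

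A reader might go further and combine the pilot's any-test and both-period rates to predict how far the GEE would inflate the standard HBST effect or shrink eTEST's. The documents do not support that. The any-test rates cover participants to date, while the both-period rates cover only the 63% who completed Month 5 (0.63 × 73 ≈ 46 people across three arms). The pilot figures also span two quarters, where a 28-point any-test gap could move the mean by 28/2 = 14 points, against 7 over the trial's four.

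**Conclusion.** The point holds as a mismatch between aim and analysis. The follow-up half of Aim 1(a) has no per-participant outcome, and the one model standing in for it can be significant on one-off tests alone: about 70–94% of the time at 300 per arm and 96–100% at 667, when repeat rates are equal and any-test is 90% v 62%. These figures rest on the assumed 20–46% repeat rates and their spread over quarters, 1:1:1 allocation, two-sided 0.05, and no site or covariate terms. They show what can happen and do not forecast this trial's result. The structural argument in steps 1, 4 and 5 needs none of these assumptions.

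It does not follow that the GEE is wrong or should go. It should not be the sole basis for a claim about repeat testing.

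**What to change.** - Keep the GEE and name it as the measure of testing frequency. State period and condition-by-period terms in it.
- Add a per-participant repeat outcome: tested in at least two of the four quarters, with tested in all four as a companion. Analyse it with the same condition-by-site logistic model as any-test, and base the follow-up/repeat conclusion on it. The two-quarter threshold is the better lead, because the plan sets missing quarterly assessments to zero and a single missed survey would fail the all-four outcome.
- Do not use a proportional-odds model of quarters tested (0–4) for this conclusion. It includes the step from none to one, and its rank-test form rejected in about 91–100% of runs with equal 46% repeat rates.

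The cost is SAP wording and one or two extra models on data the quarterly surveys already collect. The downside is lower power for the repeat outcome, as in step 6: adequate across sites at about 667 per arm for a difference like 54% v 46%, but not at 300 per arm or within a single site. The SAP should say that site-specific repeat results are descriptive.

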## B.2 Participant Population

Eligible participants will be (1) biological males, who (2) report any of the following in the past six months: anal sex without condoms outside of a monogamous partnership with a recently tested, HIV-negative male, having been diagnosed with an STI, or being in an ongoing sexual partnership with an HIV-positive male, and who (3) are not currently on PrEP. We chose to focus our study on male participants because epidemiological evidence suggests that MSM are disproportionately affected by HIV, and thus in need of tailored interventions for increasing HIV testing. These criteria are inclusive of transgender women, however. While we realize that there may be too few transgender participants to facilitate subgroup analyses, we elected to be inclusive because of the clear public health relevance of these individuals. Risk criteria were chosen to align with DHHS's PrEP criteria to allow comparisons with other PrEP studies. Eligible participants will also (4) have not tested for HIV in the last 12 months, (5) have a stable residence in one of the site metros where they can securely receive packages, (6) use an iOS/Android smartphone with a data plan or home wifi, and (7) be fluent in either English or Spanish. We will strive to recruit AA and H/L MSM at rates similar to each site's general population, but will also implement procedures specifically to attract/retain AA and H/L MSM, including consulting with local ethnic/minority community advisors about recruitment, targeting apps catering to AA and H/L MSM (e.g., Jack'd), matching race/ethnicity in ad materials, emphasizing participants' rights and community benefits in informed consent, and recruiting AA and H/L staff/counselors.

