#### **Experimental Conditions**

Only enhanced eTest participants will download the eTEST app. For these participants in the eTEST group, four HBST kits will be fit with BLE sensors and sent to participants. Follow-up calls will be made to these participants within 24 hours of opening their test to provide post-test counseling, referral for services, and a focused discussion on PrEP. In the standard HBST condition, four standard HBST kits will be sent at the same intervals, but will not be monitored and no follow-up calls will be provided. Standard participants will have a list of local resources (in Boston/Providence, L.A., or Jackson) depending on where participants are located included in the box with their test kit. This list of resources includes HIV/STD testing clinics, alcohol/drug and mental health treatment referrals, and the number for the national suicide prevention hotline,

as well as study staff contact information. These kits also, include a 24 hour helpline that participants can call with any questions or needs. In the control condition, participants will be reminded to get tested at a local clinic via text messages. Texts will link to the list of local clinics near them that conduct HIV testing, as well as their contact information/hours.

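### Every Aim 1(a) HIV-testing model adjusts for PrEP initiation, a post-randomisation event that eTEST is meant to raise, and no model without it is stated

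*Combined protocol and SAP*

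**What the plan says.** Planned Analyses gives two models for Aim 1(a): a logistic regression for any HIV test over 12 months and a GEE for testing in each 3-month period. For all models of HIV testing, "a covariate reflecting whether a given participant had initiated PrEP (and when, for longitudinal models) will be added to each model". The reason given is "since these individuals are required to test for HIV quarterly as a part of ongoing PrEP care", and the stated purpose is: "Doing so will allow us to estimate the effects of study arm on HIV testing among those who did not initiate PrEP". The plan then points to 54 surplus participants per site (162 in total) and concludes "we believe we will be fully powered to test this model, even with a high rate of PrEP adoption".

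Four other places bear on this:

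- Specific Aim 1 (B.1): "To test whether the eTEST intervention results in higher rates of (a) initial and follow-up HIV testing". It is not limited to people who stay off PrEP.
- Specific Aim 2 (B.1): whether PrEP counselling during eTEST contacts "results in more participants (a) consulting with medical providers about PrEP and (b) initiating PrEP".
- B.2 Participant Population: entrants "are not currently on PrEP".
- Experimental Conditions (B.4): eTEST participants are called "within 24 hours of opening their test to provide post-test counseling, referral for services, and a focused discussion on PrEP". Standard HBST participants get no follow-up calls, and controls get text reminders only.

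**The concern.** Because nobody is on PrEP at entry, initiation is always a post-randomisation event, and one that the eTEST arm is built to increase. Conditioning on it causes three problems.

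1. **Quarterly GEE.** Testing that eTEST produces by moving people onto PrEP is part of its effect on testing. The covariate takes that part out.
2. **Selection.** If a common trait, such as health-seeking, drives both PrEP uptake and testing, then eTEST draws more of the likely testers into the initiator group. Non-initiators are then no longer comparable between arms.
3. **Any-test model.** An eTEST participant who starts PrEP after a counselling call has already opened a kit. The covariate can therefore follow the outcome that it adjusts.

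At stake is the answer to Aim 1(a). As written, the plan would report a contrast that randomisation does not protect and would give no estimate of the effect of assignment in all participants.

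**Working it through.** **The plan's own figure.** Power Considerations gives 246 required and 300 proposed per site: 300 − 246 = 54, and 54 × 3 = 162. This reproduces. The 246 cannot be checked, because the parameters in Table 2 are not in the text. A surplus of participants improves precision and does not remove bias from conditioning on a post-randomisation event.

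**Is there a model without the covariate?** The intent-to-treat sentence in Planned Analyses concerns data from dropouts and withdrawals and leaves the covariate in place. The comparison of verified service use under Clinic records is exploratory and has no stated model. Neither supplies the missing estimate.

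**Inputs (pilot results, B.1).** Any test: eTEST 96%, standard HBST 90%, control 62%. PrEP started: eTEST 10%, control 4%. No rate is given for standard HBST, so 0–8% is assumed. Arm size is 2000/3, about 666, assuming equal allocation.

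**Any test.** Let p be the any-test rate and q the initiation rate. If every initiator tests, the adjusted arm effect is the one in non-initiators, with odds (p − q)/(1 − p).

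- Unadjusted odds: eTEST 0.96/0.04 = 24; standard 0.90/0.10 = 9; control 0.62/0.38 = 1.632. Odds ratios: 24/1.632 = 14.7 and 24/9 = 2.67.
- Adjusted odds: eTEST (0.96 − 0.10)/0.04 = 21.5; control (0.62 − 0.04)/0.38 = 1.526. Odds ratio 14.1.
- Standard HBST at q = 0, 4, 8%: odds 9.0, 8.6, 8.2. Odds ratios 2.39, 2.50, 2.62.
- Risk difference in non-initiators, eTEST v control: 0.86/0.90 − 0.58/0.96 = 35.1 points, against 34.0 overall. For eTEST v standard it is 5.6–6.4 points, against 6.0.
- Power at 666 per arm (Wald test, 40,000 simulated trials): eTEST v control 100% either way; eTEST v standard 99% unadjusted and 97–99% adjusted.

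Two checks on these figures. If only 95% of initiators test, the adjusted eTEST v standard odds ratio is 2.64–2.75, so there is no real shrinkage. Part of the movement is also non-collapsibility of the odds ratio: with equal 4% initiation in both arms, eTEST v control would be (0.92/0.04)/(0.58/0.38) = 15.1 instead of 14.7.

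**Higher uptake (assumed).** Pilot calls did not cover PrEP and trial calls will, so 10% may be low. Taking the pilot consultation rate of 25% as initiation, eTEST odds are (0.96 − 0.25)/0.04 = 17.75. The eTEST v standard odds ratio is then 17.75/9.0 = 1.97 to 17.75/8.6 = 2.06. With 4% initiation in standard HBST, power is 88%.

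**Quarterly testing.** This was simulated with 2,000 trials per scenario, four quarters and an independence GEE with clustered standard errors and quarter terms. A testing trait has log-odds 1 per SD. PrEP uptake is 10% v 4%, with log-odds 1 per SD of that trait (shared) or 0 (not shared), and the start quarter is uniform. The direct odds ratio, conditional on the trait, is 1.25, with 666 per arm. All on-PrEP quarters count as tested unless stated. Ranges cover the ever-initiated and time-varying forms of the covariate.

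| Base quarterly testing | Shared trait | Power without covariate | Power with covariate |
|---|---|---|---|
| 46% | yes | 91% | 55–66% |
| 68% | yes | 83% | 53–62% |
| 46%, 90% of on-PrEP quarters tested | yes | 89% | 53–62% |
| 46% | no | 96% | 75–76% |
| 68% | no | 89% | 70–71% |

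In the first row the odds ratio falls from 1.26 to 1.15–1.17. The risk difference is 5.8 points overall and 4.0 off PrEP. Without a shared trait, the gap is simply that between a total and a direct effect. At a direct odds ratio of 1.5, power is about 98–100% in every model.

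Both base rates are assumptions. The pilot gives 46% of controls testing in both of two quarters, and 68% is the square root of 0.46, the per-quarter rate if quarters were independent.

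**The case against.** The strongest reply is that the choice is disclosed and reasoned. PrEP care mandates quarterly tests, and separating those from tests prompted by the programme is a legitimate question. PrEP uptake has its own analysis under Aim 2. That justifies reporting such an analysis, but not as the only answer to Aim 1(a). Naming non-initiators as the target does not make the comparison a randomised one.

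On mechanism, the route from eTEST through PrEP to a first test is nearly empty, because the call follows the opening of a kit. This stands: loss of PrEP-mediated testing is a matter for the GEE, while in the any-test model the problem is ordering and selection. A main-effect covariate also keeps every participant in the model. It isolates non-initiators only if all initiators test, and otherwise assumes a common arm effect. So the model does not in general deliver the plan's stated target either.

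On materiality, the GEE is introduced as exploring regular testing, although Aim 1(a) itself includes follow-up testing. Power falls materially only over a narrow range of effects: at 46% base with a shared trait, a direct odds ratio of 1.35 already gives adjusted power of 86–92%, and 1.4 gives 93–96%. Pilot repeat-testing rates (92% v 54% and 46%) imply odds ratios of about 10 to 13.

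The base rates also fit the pilot poorly. With the assumed trait, 46% per quarter implies about 25% testing in both of two quarters, not 46%. A rate of 68% implies about 96% testing at least once over four quarters, against the pilot control rate of 62% at any time. These points limit the size of the problem. They do not supply the missing model.

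**Conclusion.** The point holds: the plan is wrong as written and should be changed. Both Aim 1(a) models condition on something the intervention is designed to alter, and no model estimates the effect of assignment on testing in all participants.

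The numerical consequence is conditional. At pilot-sized effects and pilot PrEP uptake, estimates shift slightly and conclusions do not alter. If the true effect on quarterly testing is modest, the adjusted GEE could miss an effect that the model without the covariate would probably detect. That second statement rests on the assumed direct odds ratio, base rates and trait strength. The finding about the estimand rests on the text alone.

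**What to change.** In Planned Analyses, make the any-test logistic model and the quarterly GEE primary without the PrEP-initiation covariate, adjusting for site and baseline covariates only. Report the PrEP-adjusted model as a labelled secondary, non-randomised analysis, and reword the sentence about effects among non-initiators to say so. Drop the 54-per-site surplus as an answer to this issue.

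If testing outside PrEP care is of interest, the quarterly surveys already ask whether each test was linked to PrEP care. That item could define a secondary outcome without conditioning on initiation.

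The cost is SAP wording and one extra reported model, with no new data and no change to trial conduct.
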